1994) will be administered prior to oral dose administration, again at approximately 6 hours post-dose (approximate peak concentration) and approximately 24 hours post-dose.

If a participant is found to be depressed, a clinician will perform further assessment and refer the participant to care as necessary. As part of ongoing adverse event monitoring, participants will be asked about changes in mood during in-person and phone visits. Additionally, they will be advised to call to inform the study team of changes in mood, specifically depression, between visits.

Blood will be collected for safety laboratory studies prior to drug dose administration and on Days 2 and 3. Safety laboratory studies will include a comprehensive metabolic panel [glucose, blood urea nitrogen (BUN), creatinine, sodium, potassium, chloride, bicarbonate, calcium, total protein, albumin, total bilirubin, alkaline phosphatase, aspartate transaminase (AST), alanine transaminase (ALT)], phosphate, a lipid panel [total cholesterol, low density lipoprotein (LDL), high density lipoprotein (HDL), triglycerides], a complete blood count and differential, lactate acid dehydrogenase (LDH), creatine kinase (CK), amylase, and a urinalysis with reflex microscopic examination.

Plasma will be collected for PK analysis as shown in [Table 4](#).

A 24-hour urine collection will be performed starting at the time of study drug administration. A second 24-hour urine collection will be performed from 24-48 hours after study drug administration. These samples will be used to measure urine drug and metabolite levels.

The participant will remain in the HRU on Study Days 1 and 2, and discharged on Study Day 3 after all required assessments have been completed. During the inpatient stay, abnormal assessments and laboratory values will be evaluated by the PI in collaboration with the medical monitor in real time. See the schedule of events ([Table 3](#)) for details on the assessments on each Study Day.

Post Treatment Follow-up Visits

See the schedule of events ([Table 3](#)) for details on the assessments on each Study Day.

Visit 3 (Day 4) – Vital signs (BP, pulse, respiratory rate, and oral body temperature) will be obtained. Plasma samples for PK assessments will be collected. Information on changes or newly administered concomitant medications as well as any new or ongoing (S)AEs will be collected at each visit.

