Adverse event (AE): An adverse event (AE) is any adverse change from the participant's baseline condition, regardless of relationship to study drug, including clinical or laboratory tests, or abnormalities which occur after informed consent is signed and up to 7 days after the study drug has been discontinued. Clinically significant adverse changes in clinical status, ECGs, and physical examinations are considered AEs. Any participant complaint associated with such an abnormal finding will also be reported as an AE. AEs are only collected upon the start of study drug. Events occurring prior to this are to be reported as part of the participant medical history. However, SAEs are to be collected from the time of informed consent.

Adverse events include but are not limited to: (1) worsening or change in nature, severity, or frequency of conditions or symptoms present at the start of the study; (2) participant deterioration due to primary illness; (3) intercurrent illness; and (4) drug interaction. An abnormal laboratory value will only be reported as an AE if it requires therapeutic medical intervention, if the investigator considers it to be an AE, or if it leads to the participant being withdrawn from the study.

The investigator should attempt to establish a diagnosis of the event based on signs, symptoms, and/or other clinical information. In such cases, the diagnosis should be documented as the AE and not the individual signs/symptoms. Symptoms and conditions present at the beginning of the study will be characterized, so that AEs can be defined as any new symptom, or any increase in frequency or severity of an existing symptom.

Following questioning and evaluation, all AEs, whether determined to be related or unrelated to the study drug by the Site Protocol Principal Investigator, must be documented in the participant's medical records, in accordance with the investigator's normal clinical practice. Each AE is evaluated for duration, severity, seriousness, and causal relationship to the study drug.

The intensity of each AE will be rated according to the following 3-point scale:

- **Mild**: Awareness of signs or symptoms, but no disruption of usual activity
- **Moderate**: Event sufficient to affect usual activity (disturbing)
- **Severe**: Inability to work or perform usual activities (unacceptable)

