Serious Adverse Event (SAE): Any untoward medical occurrence that at any dose: results in death, is life-threatening, require inpatient hospitalization or prolongation of existing hospitalization, results in persistent or significant disability/incapacity, or is a congenital anomaly/birth defect (NIH Guide-6/11/99).

Note 1: Medical and scientific judgment should be exercised in deciding whether expedited reporting is appropriate in other situations, such as important medical events that may not be immediately life-threatening or result in death or hospitalization but may jeopardize the participant or may require intervention to prevent one of the outcomes listed in the definition above.

Note 2: Hospitalizations that fulfill one of the following conditions will not have to be reported as SAE:

- Hospitalizations for social reasons and thus unrelated to a deterioration of the participant's condition or adverse event (e.g., deterioration of the living conditions related to environmental factors rather than to a deterioration of the disease, lack of transportation to the investigational site, respite care for the caregiver)
- Hospitalizations for elective surgical interventions for which the date had already been determined prior to the study participation.

Unlisted (Unexpected) adverse event: An adverse event, the nature or severity of which is not consistent with the applicable product information (e.g., package insert/summary of product characteristics for an approved product (ICH and GCP)).

Life-Threatening: Any event in which the participant was at risk of death at the time of the event; it does not refer to an event, which hypothetically might have caused death if it were more severe.

Associated with the use of the drug: An adverse event is considered associated with the use of the drug if the attribution is possible, probable, or definite.

Abnormal Test Findings

The criteria for determining whether an abnormal objective test finding should be reported as an AE are as follows:

- test result is associated with accompanying symptoms, and/or
- test result requires additional diagnostic testing or medical/surgical intervention, and/or
- test result leads to a discontinuation from the study, significant additional concomitant drug treatment, or other therapy, and/or
- test result is considered to be an AE by the investigator in consultation with the medical monitor.

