No inferential statistical testing is planned. However, if used for exploratory analysis, inferences will be assessed against a 5% alpha, and therefore p-values ≤ 0.05 will be considered statistically significant. All tests will be two-sided. No adjustment will be made to p-values for multiple testing.

Participant Disposition and Exposure

The numbers of participants completing or withdrawing, along with reasons for withdrawal, will be summarized by dose.

Tabulation of the number of doses of study drug, duration of treatment as well as total dose given will be provided.

Demographics and Baseline Characteristics Analyses

Demographic variables (age, sex, race, and ethnicity) as well as height (cm), weight (kg), Body Mass Index (BMI), temperature, heart rate, blood pressure and respiratory rate or pulse oximetry (from the vital signs) at baseline will be summarized using descriptive statistics. All demographic data will be provided in a data listing.

Efficacy Endpoints

No efficacy endpoints will be assessed since this is a sample of healthy participants.

Safety Endpoints

The safety analysis will be descriptive in nature. All safety data will be listed, and data will be tabulated by dose. Safety data include:

- AEs
 - Events occurring prior to the first dose of study drug will be defined as pre- treatment events.
 - TEAEs will be defined as any AE occurring during or after oral administration of the study drug. Therefore, this will include all events occurring through Day 7/ET.

Incidence of AEs will be summarized for each cohort by MedDRA system organ class (SOC) and preferred term (PT), sorted in descending frequency by SOC, and then by PT within SOC. These summaries will be given by dose in separate tables for each of the following TEAE event sets:

- All events

- Treatment related events (defined by a relationship to study drug of possible, probable, or definite).
- Serious adverse events
- Events leading to premature discontinuation from study
- Events by maximum severity
- AEs of Special Interest, ie, events relating to cognitive decline or neuropsychiatric symptoms.

Other safety outcomes will include:

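### The only AE intensity scale has no anchor for size, so a large but silent laboratory or ECG adverse event is rated no higher than Mild unless someone judges that it affects activity

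*Combined protocol and SAP*

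**What the plan says.** Section I, item 12, Plan for Grading Adverse Events: "The intensity of each AE will be rated according to the following 3-point scale". Mild is "Awareness of signs or symptoms, but no disruption of usual activity". Moderate requires an effect on usual activity, and Severe requires being unable to work or to carry out usual activities. No other grading scale is named.

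The same section defines what is rated: "Clinically significant adverse changes in clinical status, ECGs, and physical examinations are considered AEs". A laboratory value becomes an AE if it needs treatment, if the investigator considers it one, or if it leads to withdrawal. Abnormal Test Findings gives a list of alternatives. Accompanying symptoms are one; another is "test result requires additional diagnostic testing or medical/surgical intervention, and/or".

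Item 13, Safety Endpoints, tabulates six TEAE event sets by dose, one of which is "Events by maximum severity".

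Item 4, In-patient Treatment: "The participant will remain in the HRU on Study Days 1 and 2", with discharge on Day 3.

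**The concern.** Two parts of the safety plan do not fit together. The AE definition admits objective findings without symptoms. The intensity scale measures only what the participant notices or can no longer do. A marked QTc prolongation and a slight but clinically significant one, both silent, would receive the same rating. So would a large and a small transaminase rise.

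Safety and tolerability form part of the primary objective, and each dose has only six participants. The maximum-severity table is where a reader would look for AEs that become worse with dose. For silent laboratory and ECG events, that table may carry no information about size.

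**Working it through.** The plan states no figure on this point, so the check sets its provisions side by side.

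1. **Can a symptom-free finding be an AE?** Yes. Clinically significant ECG changes qualify directly. Laboratory results qualify through treatment, investigator judgement, withdrawal or further diagnostic work. Symptoms are one route among several, not a condition.

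2. **Must it be rated on this scale?** Yes. The scale covers each AE, and there is no separate laboratory or ECG scale.

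3. **Which level can it reach?** Moderate and Severe both require an effect on activity or work. Without one, only Mild is left. Mild itself speaks of awareness of signs or symptoms, so a silent finding fits it only if an objective abnormality is read as a sign. No level refers to the size of the change or to the need for intervention.

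4. **When do these findings arise?** The scheduled post-dose ECGs are at about 6, 24 and 48 hours (Table 3, footnote 5), all within the inpatient stay. Table 3 places post-dose safety laboratory draws on Days 2, 3 and 7, so two of the three fall within the stay. (The Follow-Up paragraph can be read as adding a Day 4 draw, which would make it two of four.) The protocol puts approximate peak concentration at 6 hours. Work and usual activity are hard to judge for someone confined to a research unit, and this applies to symptoms there as well.

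5. **Where does the rating go?** It goes into the maximum-severity set, one of the six. The other five (all events, treatment-related, serious, leading to discontinuation, special interest) do not depend on it. The DSMB reviews non-serious AEs after each cohort. The layout of those summaries is not given, so the rating matters there only if it is shown.

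6. **What else shows the size of such changes?** Safety Endpoints plans laboratory changes over time, incidence of new-onset potentially clinically significant (PCS) values, a similar analysis of ECG parameters, and shift tables for heart rate and QTc. The PCS ranges are still to be defined.

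7. **Does any rule use the grade?** No. Escalation uses AUC bands together with serious AEs or other safety concerns. Stopping rests on the judgement of the PI and medical monitor.

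**How often could it matter?** The documents give no rate for such events. If a fraction p of participants at a dose had one, the chance of at least one in a cohort of 6 would be 1 − (1 − p)^6:

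| Assumed p | At least one in 6 |
|---|---|
| 5% | 26.5% |
| 10% | 46.9% |
| 20% | 73.8% |
| 30% | 88.2% |

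These rates are assumptions. The table shows only how often a cohort would contain an event that needs such a rating, not how far any rating would be wrong.

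**The case against.** The strongest reply is that little depends on this scale. The summaries in step 6 show the size of laboratory and ECG changes, and QTc has its own shift table. The DSMB also receives other safety data in summary tables. Non-serious AEs larger or more frequent than anticipated must be reported to it within 48 hours, a route that does not use the intensity scale. During the stay, the PI and medical monitor assess abnormal values as they arise. Seriousness is judged separately, and a finding that prolongs hospitalization is an SAE. An investigator may reasonably decide that a silent finding needing treatment affects usual activity and rate it higher. TEAEs run to Day 7, so some ratings reflect life after discharge.

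All of this stands, and it rules out two stronger readings. A reader might infer that a dose-related rise in laboratory or ECG toxicity would be invisible to the DSMB; the separate summaries and the 48-hour reporting contradict that. A reader might also infer that dose escalation is compromised; no escalation rule refers to the grade.

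The reply does not repair the rating itself. PCS incidence is a yes/no count with no ranges yet given, and none of these routes changes what enters the severity table. Upward rating by judgement is possible, but without guidance it may differ between raters and cohorts.

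**Conclusion.** The point holds as a defect in AE severity reporting. If silent laboratory or ECG AEs occur and the scale is followed as written, the maximum-severity table, and any DSMB summary that carries the rating, can understate their severity. Where the error arises from this rule, it is towards too low a rating.

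Its size cannot be estimated. It is tempting to say that one misrated participant moves a cohort's row by 1/6 = 16.7 percentage points, but that is the resolution of any table with six per row. It would measure this defect only if such an event occurred and deserved a higher grade, and the documents give no basis for either.

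It is a cheap improvement worth making, because safety is a primary objective and the table is already planned. It does not show that the trial's safety monitoring fails.

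**What to change.** Keep the 3-point scale for symptomatic AEs. For laboratory, ECG and vital-sign AEs, assign Mild, Moderate or Severe by magnitude tiers that the sponsor sets and writes down before the first cohort is summarised. The PCS ranges that Safety Endpoints already requires are the natural starting point. They are stated for laboratory tests and, by extension, ECG parameters, so vital-sign limits would need to be added. Add a short instruction on how to rate symptoms that arise on the unit, where work and usual activity do not apply directly. Use these ratings in the maximum-severity table and in the DSMB summaries.

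The cost is one table of limits and one CRF instruction, with no new measurement. The downside is that some AEs will be rated more severe than under the present wording.

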Exploratory endpoints will include drug receptor occupancy assessment with [¹⁸F]FPEB PET by comparing within-participant changes in mGluR5 availability pre-treatment and at the time of presumed maximal brain drug concentration. This analysis will be performed in a subset of 2 participants per dose cohort for the 10-100 mg dose levels. PET scans may occur in a subset of 2 participants per cohort for dose level 150 mg and 200 mg.

Pharmacokinetics

Plasma samples will be collected for analysis, as shown in Table 4. The timing for plasma sample collection may be adjusted for subsequent cohorts based on PK data from the preceding cohorts.

Table 4: Schedule for Pharmacokinetic Sampling*

	Day 1 (Dosing day)	Day 2	Day 3	Day 4	Day 7
Plasma Samples	Pre-Dose, and post-dose at 30 min (\pm 10 min), 1 h (\pm 10 min), 2 h (\pm 10 min), 4 h (\pm 10 min), 8h (\pm 1 h), 12 h (\pm 1 h)	24 h (\pm 1 h)	48 h (\pm 2 h)	72 h (\pm 6h)	Day 7 \pm 1 day
Urine Samples	24 hour collection starting immediately post-dose	Second 24 hour collection from 24 to 48 hours post-dose			

*Participants in the receptor occupancy sub-study will have up to five additional PK samples collected during each PET scan. The timing of these samples will be with respect to [¹⁸F]FPEB injection as follows: within 10 minutes prior to tracer injection, 1 h after tracer injection, and 2 hours after tracer injection.

Pharmacokinetic assessment will be carried out at Aptuit (Verona) Center for Drug Discovery and Development upon shipment to:

[name]/ [name]/[name]
 Aptuit (Center for Drug Discovery & Development)
 [name]
 Email box: [contact]
 Tel: [name] or [name] or [name]

Remaining plasma and urine may be transferred to a separate (non GLP) experimental protocol wherein individual samples will be pooled and used to investigate the metabolism and excretion of study drug and related components.

Receptor Occupancy Substudy

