This MR study is for research purposes only and is not in any way a clinical examination. The scans performed in this study are not designed to find abnormalities. The PI, the lab, the MR technologist, and the Magnetic Resonance Research Center are not qualified to interpret the MR scans and are not responsible for providing a diagnostic evaluation of the images. If a worrisome finding is seen on a scan, a radiologist will be asked to review the relevant images. Based on his or her recommendation (if any), the PI or consulting physician will contact the participant, inform the participant of the finding, and recommend that the participant seek medical advice as a precautionary measure. The decision for additional examination or treatment would lie solely with the participant and the participant's physician. The PI, the consulting physician, the Magnetic Resonance Research Center, and Yale University are not responsible for any examination or treatment that the participant receives based on these findings. The images collected in this study are not a clinical MR exam and for that reason, they will not be made available for diagnostic purposes.

The MRI scans will be read by an outside neuro-radiologist ([name]) assess for exclusion criteria. In the event that [name] is unavailable for these readings, we will arrange for another qualified radiologist

to evaluate the scans.

Risks Associated with Use of an Arterial Catheter

On the PET scanning day, a radial arterial catheter will be inserted. Certain individuals may feel light-headed during arterial catheter placement. Arterial catheter placement may be associated with mild-to-moderate pain, hematoma, inflammation, bleeding, or bruising at the puncture site. If any of these, or other symptoms occur and do not diminish within 24 to 72 hours after the arterial line removal, or in the event that they worsen, subjects will be advised to call the on-call doctor listed on the PET discharge instructions. In rare instances, blocking of the artery, tearing of the artery, arterial leakage, poor healing, nerve damage, or infection at the catheter insertion site may occur.

Risks Associated with Radiation

The RSC will review the use of radiation in this research study, and no participants will be scanned until approval is obtained. This research study involves exposure to radiation from [¹⁸F]FPEB and associated transmission scans or low dose head CTs.

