The PI and medical monitor may elect to stop dosing or stop the study based on any treatment emergent concerns. Although not expected based on animal toxicology and PK studies, participants will be monitored for clinically significant neuropsychiatric symptoms with the GDS and NPI-Q, neurological symptoms by exam, cognitive toxicity with testing, and laboratory abnormalities. While the planned doses are below the human equivalent of the repeated doses which caused serious adverse effects with lethargy in rat, participants will be monitored by frequent repeated GCS observations. Dosing may be stopped due to the occurrence of any individual adverse events which, in the judgment of the PI and medical monitor, need further characterization with respect to progression and reversibility before further dosing is conducted. Such adverse events may include non-serious unusual events. If dosing is stopped, review of the data by the medical monitor and DSMB must occur with a positive recommendation before dosing can be resumed.

Attribution of Adverse Events

- Definite: Adverse event(s) will clearly be related to investigational agent or other intervention and cannot be reasonably explained by an alternative explanation – i.e., concomitant drug(s), concomitant disease(s). The relationship in time is very suggestive.
- Probable: Adverse event(s) will likely be related to investigational agent. The relationship in time is suggestive that the adverse event is likely related to the investigational agent. An alternative explanation is less likely – i.e., concomitant drug(s), concomitant disease(s).
- Possible: Adverse event(s) may be related to investigational agent. An alternative explanation – i.e., concomitant drug(s), concomitant disease(s), - is inconclusive. The relationship in time is reasonable; therefore, the causal relationship cannot be excluded.
- Unlikely: Adverse event(s) will doubtfully be related to investigational agent(s). An adverse event for which an alternative explanation is more likely – i.e., concomitant drug(s), concomitant disease(s), and/or the relationship in time suggests that a causal relationship is unlikely.
- Unrelated: Adverse event(s) will clearly not be related to the investigational agent

Plan for Grading Adverse Events

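### The Definite attribution level reaches beyond the study drug, so a post-dose arterial-line or PET event can be filed as treatment related

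*Combined protocol and SAP*

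**What the plan says.** **Event sets.** Section 13 (Safety Endpoints) states: "TEAEs will be defined as any AE occurring during or after oral administration of the study drug", and takes this through Day 7 or early termination. Under Plan for Grading Adverse Events in Section 12, an AE is any adverse change "regardless of relationship to study drug". Section 13 then lists by-dose tables, among them all events and a set described as "Treatment related events (defined by a relationship to study drug of possible, probable, or definite".

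**Attribution.** Section 12 (Attribution of Adverse Events) has five levels. The top one reads: "Definite: Adverse event(s) will clearly be related to investigational agent or other intervention". It adds that no alternative explanation should be reasonable, and names only concomitant drugs and diseases as alternatives. The other four levels refer to the agent alone; the lowest reads: "Unrelated: Adverse event(s) will clearly not be related to the investigational agent". On assessment, Section 12 says: "Each AE is evaluated for duration, severity, seriousness, and causal relationship to the study drug". It also treats Possible, Probable and Definite events as associated with use of the drug.

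**Procedures after dosing.** Receptor occupancy participants have scans at about 4 and 24 hours after the dose (Table 3, footnote 9), with a radial artery catheter where one can be placed (PET Scan Procedures). AEs are recorded throughout each PET visit. Section 10 warns: "Arterial catheter placement may be associated with mild-to-moderate pain, hematoma, inflammation, bleeding, or bruising at the puncture site", and also mentions light-headedness at placement.

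**Participation.** Section 4 (Efficacy) plans PET in 2 participants per cohort at 10-100 mg. For the two highest doses it says: "PET scans may occur in a subset of 2 participants per cohort for dose level 150 mg and 200 mg".

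**The concern.** The attribution scale is the only device in the plan that separates drug effects from procedure effects, and its top level does not do so. The person rating a catheter event has two levels that both fit, and the choice decides whether the event appears in the treatment-related table. Nothing else in the plan recovers the distinction. Causality is judged against study drug only, no procedure or tracer relationship is captured, and the rule that events after tracer administration go to the PET center is a reporting route, not an analysis category.

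This matters because safety is part of the primary objective and there is no control group, so the comparison across doses is the main internal evidence on AEs. If scanned participants are spread unevenly over the doses, procedure events add to some cohorts and not to others.

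**Working it through.** The plan gives no AE rate and no power calculation, so there is no stated figure to reproduce.

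**Step 1. Apply the scale to a clear case.** Take a puncture-site haematoma after the 24-hour scan, plainly caused by the line.

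| Level | Refers to | Fits? | Consequence |
|---|---|---|---|
| Definite | agent or other intervention | Yes; no concomitant drug or disease explains it | treatment-related table; associated with the drug |
| Unrelated | agent only | Yes | neither |

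Under either rating the event is in the all-events table, because that set is defined by timing.

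**Step 2. Size in the all-events table.** Inputs:
- 6 participants per cohort (Table 1).
- k = number scanned: 2 planned at 10-100 mg; 0 or 2 at 150 and 200 mg (Section 4, Efficacy).
- b = risk of a TEAE apart from PET procedures: assumed 0.10-0.50.
- q = risk of at least one procedure event over the two post-dose sessions, per scanned participant: assumed 0.10-0.50, independent of b.

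Expected any-TEAE incidence = b + (k/6)(1 - b)q. The gap against an unscanned cohort is (k/6)(1 - b)q, or k(1 - b)q participants. The factor (1 - b) is there because a participant with both kinds of event counts once.

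For k = 2 against k = 0:
- Smallest: (2/6)(0.50)(0.10) = 0.017, or 1.7 points; 2 × 0.50 × 0.10 = 0.1 participant.
- Largest: (2/6)(0.90)(0.50) = 0.150, or 15.0 points; 2 × 0.90 × 0.50 = 0.9 participant.

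At b = 0.20:

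| q | k = 0 | k = 2 | Gap (points) |
|---|---|---|---|
| 0.10 | 20.0% | 22.7% | 2.7 |
| 0.30 | 20.0% | 28.0% | 8.0 |
| 0.50 | 20.0% | 33.3% | 13.3 |

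**Step 3. Effect on a dose contrast.** Assume non-procedure rates of 20% at 10-100 mg and 30% at 150 and 200 mg, a true rise of 10 points. Lower doses have k = 2 throughout.

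| q | Rise seen, k = 0 at high doses | Rise seen, k = 2 at all doses |
|---|---|---|
| 0.10 | 30.0 - 22.7 = +7.3 | 32.3 - 22.7 = +9.7 (unrounded) |
| 0.30 | 30.0 - 28.0 = +2.0 | 37.0 - 28.0 = +9.0 |
| 0.50 | 30.0 - 33.3 = -3.3 | 41.7 - 33.3 = +8.3 (unrounded) |

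The high-dose figures in the last column are 0.30 + (2/6)(0.70)q. Unequal scanning does the damage. With equal scanning the contrast is nearly preserved, while both rates rise.

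The treatment-related table follows the same formula, with b and q restricted to events rated Possible or higher. The documents give no basis for how many procedure events would be rated that way.

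**The case against.** A timing-based TEAE set beside a drug-related set is ordinary practice. A reader might infer that the plan counts every post-dose event as drug-caused. It does not: Section 13 limits the treatment-related set to relationship to study drug, and Section 12 has each AE judged against study drug. Read as a whole, the natural rating for a catheter haematoma is Unrelated. That stands, and it makes the defect an ambiguity that can misfile an event, not a rule that always does.

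A reader might also infer that PET participation is set to differ by dose. Section 4 leaves scans at 150 and 200 mg optional, and the Receptor Occupancy Substudy section aims for two participants per cohort with no exception by dose. Imbalance is allowed, not scheduled.

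A much larger effect is tempting if one takes the substudy cap of four per cohort as the number scanned. The formula then gives 3.3-30.0 points against an unscanned cohort, and more if background events are ignored. But four is an allowance for failed tracer synthesis and scan timing, scanning stops once adequate data are in hand, and Section III gives a cap of three. An intravenous catheter may also replace the arterial line.

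Finally, the analysis is descriptive, escalation rests on AUC bands and judgement with no AE-rate rule, and listings and preferred-term tables let a reader recognise puncture-site events. This limits the consequence. It does not remove it: light-headedness at line placement is not recognisable as procedural from its term, and the first post-dose scan targets presumed maximal brain concentration, so timing does not separate the two causes.

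**Conclusion.** The attribution definition is wrong as written, with low severity. Definite extends to other interventions while Sections 12 and 13 treat it as a relationship to the drug, and no procedure or tracer relationship is recorded to resolve the conflict.

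The numerical effect on by-dose rates is conditional. For 2 against 0 scanned of 6 it is about 2-15 percentage points of any-TEAE incidence, or 0.1-0.9 of a participant. This rests on assumed background and procedure-event risks of 10-50% each, independence between them, and unequal participation. The documents do not support saying that dose comparisons are distorted, or that a trend will be reversed. They support saying that this can happen if the optional scans at the two highest doses are not done.

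**What to change.** 1. In Section 12 (Attribution of Adverse Events), limit Definite to the study drug, in line with the other four levels, the grading text and Section 13.
2. Add one CRF field for relationship to PET procedure, arterial line or tracer, completed when the event is recorded; re-attribution afterwards is weaker.
3. In Section 13, keep the all-events table and add one by-dose TEAE table that excludes events attributed only to those procedures. Show the number scanned per cohort in the column header.
4. Flag substudy status in the listings. Splitting every table by substudy status would give cells of about 2 and 4, and Section 13 already says the sample size precludes subgroup analysis.

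The cost is one CRF field and one extra table.
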